### 3.2 Exclusion Criteria

1. Any serious medical condition, laboratory abnormality, or psychiatric illness that would prevent the subject from providing informed consent.
2. Any condition, including the presence of laboratory abnormalities, which places the subject at unacceptable risk if he/she were to participate in the study or confounds the ability to interpret data from the study.
3. Evidence of laboratory TLS by Cairo-Bishop Definition of Tumor Lysis Syndrome (see Appendix D). Subjects may be enrolled upon correction of electrolyte abnormalities.
4. Concurrent use of other anti-cancer agents or treatments.

---

† A female of childbearing potential is a sexually mature woman who: 1) has not undergone a hysterectomy or bilateral oophorectomy; or 2) has not been naturally postmenopausal for at least 24 consecutive months (i.e., has had menses at any time in the preceding 24 consecutive months).

5. Prior treatment with thalidomide or lenalidomide.
6. Active serious infection not controlled with antibiotics.
7. Autoimmune hemolytic anemia or thrombocytopenia requiring treatment.
8. Known positive for HIV
9. Active infection with hepatitis B, defined by being positive for HepBsAg or Hep B DNA by PCR, or hepatitis C
10. Pre-existing peripheral neuropathy  $\geq$  grade 2
11. Pregnant or breast feeding females. (Lactating females must agree not to breast feed while taking lenalidomide and/or thalidomide).

#### **4. REGISTRATION PROCEDURES**

##### **Central Patient Registration**

[REDACTED]

[REDACTED]

[REDACTED]

Once a patient is registered onto the trial, they will need to be registered with both the STEPS® (P-TAP) and RevAssist® (RASP) programs in order to receive their thalidomide and lenalidomide. (See Appendix F for instructions.)

#### **5. TREATMENT PLAN**

##### **5.1 Overall design**

This is an open label, phase II, single arm, and single institution study investigating daily alternating IMiD™ agent therapy with thalidomide and lenalidomide plus rituximab in untreated CLL patients requiring treatment as outlined in the IWCLL update of the 1996 NCI-Working Group criteria for CLL [15]. Half of the patients (odd numbered subjects) will start with a two week course of single agent thalidomide and the other half of the patients (even numbered subjects) will start with a two week course of single agent lenalidomide in order to perform correlative studies to elucidate the

mechanisms of action of thalidomide and lenalidomide. Daily alternating IMiD™ agent therapy will begin with cycle 2 as follows:

- Cycle -1: half of the patients (odd numbered subjects) will receive thalidomide 50 mg PO daily on days 1-14, followed by no treatment days 15-28 and the other half of the patients (even numbered subjects) will receive lenalidomide PO daily on days 1-14, followed by no treatment days 15-28. The lenalidomide dose will be based on baseline calculated creatinine clearance\*.
- Cycles 1 and all escalation cycles: Patients will receive thalidomide 50 mg (every **ODD** day on Days 1-28 of a 28 day cycle: Days 1, 3, 5, 7, 9, 11, 13, 15, 17, 19, 21, 23, 25 & 27) with lenalidomide (every **EVEN** day on Days 1-28 of a 28 day cycle: Days 2, 4, 6, 8, 10, 12, 14, 16, 18, 20, 22, 24, 26 & 28). Each cycle will be 28 days in length. Patients who received lenalidomide during Cycle -1 will receive the same dose of lenalidomide starting with Cycle 1. For patients who did not receive lenalidomide during Cycle -1, lenalidomide will be initiated at a starting dose based on baseline calculated creatinine clearance\*.
- Cycle 1: Patients will also receive rituximab 375 mg/m^2 IV on Days 1, 8, 15 and 22 (+/- 2 days) and then again on the same weekly x 4 schedule every 6th cycle through Cycle 19 (Cycle 7, 13, and 19).

\*\*\*\* Rituximab can be given +/- 2days.

\*\*\*\*All correlative work must be drawn prior to Rituximab administration regardless of the day Rituximab is given.

\*The lenalidomide starting dose will be based on baseline calculated creatinine clearance as follows:

Lenalidomide Starting Dose Based on Renal Function at Study Entry	
Baseline Calculated Creatinine Clearance (by Cockcroft-Gault)	Starting Lenalidomide Dose
≥ 60 ml/min	5 mg every EVEN day during Days 1 – 28 of each 28-day cycle**
≥ 30 and < 60 ml/min	5 mg every 2 nd EVEN day during Days 1 - 28 of each 28-day cycle**

\*\*For patients who receive lenalidomide during Cycle -1, the lenalidomide dose during Cycle -1 will be at the dose indicated above (5 mg every other day or 5 mg every 2nd EVEN day depending on baseline calculated creatinine clearance) taken daily on Days 1 – 14 of the 28-day cycle.

At investigator discretion, the lenalidomide dose may be gradually increased in a step-wise manner (in 5 mg increments) at the start of any subsequent 28-day treatment cycle beginning with the start of Cycle 2, if the patient tolerated the prior treatment cycle without requiring dose modifications, interruptions or delays due to toxicity. For patients who initiate therapy at a lenalidomide 5 mg every 2nd EVEN day starting dose, the first dose titration would be to lenalidomide 5 mg every EVEN day, and subsequent dose titrations would be permitted in 5 mg increments. The lenalidomide dose may only be increased at the start of a new cycle of therapy, may only be increased once every 28 days (or less frequently), and may only be increased if the prior treatment cycle was completed without requiring dose modifications, interruptions or delays due to toxicity. For patients who initiate treatment at lenalidomide 5 mg based on baseline calculated creatinine clearance  $\geq 60$ ml/min, the maximum allowable dose is lenalidomide 25 mg every EVEN day during Days 1-28 of a 28-day cycle. For patients who initiate treatment at lenalidomide 5 mg every 2nd EVEN day due to baseline calculated creatinine clearance  $\geq 30$ ml/min but  $< 60$ ml/min, the maximum allowable dose is lenalidomide 15 mg every EVEN day during Days 1-28 of a 28-day cycle.

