**STUDY DESIGN:**

This is an open label, phase II, single arm, and single institution study investigating daily alternating therapy with the IMiD™ compounds, thalidomide and lenalidomide, plus rituximab in untreated CLL patients requiring treatment. In order to obtain correlative samples, patients will receive a two week course of single agent thalidomide or lenalidomide before beginning treatment with the combination regimen. Half of the patients (odd numbered subjects) will start with a two week course of single agent thalidomide and the other half of the patients (even numbered subjects) will start with a two week course of single agent lenalidomide. This will allow the study of correlative samples of monotherapy with either IMiD™ agent. In Cycle -1, half of the patients (odd numbered subjects) will receive thalidomide 50mg PO daily on days 1-14, followed by no treatment days 15-28. The other half of the patients (even numbered subjects) will receive lenalidomide PO daily on days 1-14, followed by no treatment days 15-28. Starting cycle 1, patients will receive thalidomide 50 mg every other day (every odd day on days 1-28: Days 1, 3, 5, 7, 9, 11, 13, 15, 17, 19, 21, 23, 25 & 27 of a 28 day cycle) alternating with lenalidomide on alternate every other day, dosed based upon current level with stepwise incremental dosing (every even day on days 1-28: Days 2, 4, 6, 8, 10, 12, 14, 16, 18, 20, 22, 24, 26 & 28 of a 28 day cycle). The starting dose of lenalidomide will be based on calculated creatinine clearance and the dose of lenalidomide may be escalated as tolerated to maximal dose of 25 mg (see Section 5 for details). Rituximab 375 mg/m^2 will be administered on days 1, 8, 15 and 22 starting with Cycle 1 and then again on the same weekly x 4 schedule every 6th cycle through Cycle 19 (Cycles 7, 13, and 19).

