**STUDY DURATION:** 3 years**TOTAL SAMPLE SIZE:** 24 patients**DOSING REGIMEN(S):**

**Cycle -1:** thalidomide 50 mg PO daily on days 1-14 or lenalidomide PO daily on days 1-14 of a 28 day cycle (odd numbered subjects will receive thalidomide and even numbered subjects will receive lenalidomide). Days 15-28 no drug treatment.

**Starting on Cycle 1:** Alternating every other day thalidomide 50 mg (every ODD day on days 1-28: Days-1,3,5,7,9,11,13,15,17,19,21,23,25 & 27 of a 28 day cycle) with lenalidomide (every EVEN day on days 1-28: Days-

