### **1.2. Secondary Objectives**

- To determine the safety, tolerability, and feasibility of combining thalidomide, lenalidomide, and rituximab as initial treatment for patients with CLL requiring therapy.
- To evaluate duration of response, time to response, progression free survival and overall survival
- To perform correlative studies to determine the potential mechanism of action of how thalidomide and lenalidomide are affecting CLL lymphocytes.

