### 3. Impact of IMiD therapy on TNF Family and cox Family mRNA stability\*:

- 1) Impact on p38 MAPK activity: day 1, 15 of cycles -1 and 1 prior to administration of study drugs

- 2) TNF-alpha / cox-2 / BAFF mRNA levels: day 1, 15 of cycles -1 and 1 prior to administration of study drugs
  - 3) Level of HuR binding to TNF-alpha / cox-2 mRNA / BAFF mRNA: day 1, 15 of cycles -1 and 1 prior to administration of study drugs
4. RNA Expression Arrays\*
- Changes in RNA expression resulting from the IMiD therapy will be assessed using RNA expression arrays. Samples to be assessed:
- 1) CLL cells: day 1, 2, and 15 of cycles -1 and 1 prior to administration of study drug
  - 2) T cells: day 1, 2, and 15 of cycles -1 and 1 prior to administration of study drug
  - 3) Monocytes: day 1, 2, and 15 of cycles -1 and 1 prior to administration of study drug
5. Methylation Arrays\*
- Changes in gene methylation patterns resulting from IMiD therapy will be assessed using methylation oligomicroarrays (MOMA) at:
- Day 1 and 15 of cycles -1 and 1 prior to administration of study drug
6. Metabolomics\*: day 1, 15 of cycles -1 and 1 prior to administration of study drug
7. Peripheral Blood Activation Markers\*
- Changes in cell surface markers will be assessed by flow cytometry and will include: CD38, HLA-DR, CD25: Prior to administration of study drug in Cycle -1, 1 and 2 on Days 1 and 15.
8. Peripheral Blood Cell Subset Analysis\*
- Changes in peripheral blood mononuclear cell subsets: baseline; Cycle 1 prior to administration of study drug on days 1 and 15 ; Cycles 2 and 3 prior to administration of study drug on Day 1; every three cycles for Cycle 6 through Cycle 24; followed by every six cycles thereafter.
- Panel to include:
- CD3/CD4/CD8: T cell subsets
  - CD16/CD56: NK cells
  - CD14: monocytes
  - CD3/CD25/FoxP3: regulatory T cells
  - Circulating Endothelial cell precursors
9. VEGF Analysis\* prior to administration of study drug in Cycles -1, 1 and 2 on Days 1 and 8.
- 1) VEGF, bFGF serum levels
  - 2) Changes in VEGF Receptor expression profile

10. Genetic polymorphisms predictive of response\* prior to administration of study drug in Cycles -1, 1 and 2 on Days 1 and 15.

- 1) TNF-alpha
- 2) BAFF

11. T-cell Repertoire Studies: samples will be collected prior to treatment on cycle -1 and prior to cycles 6, 12, and 24 and evaluated for T-cell Repertoire

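### The Cycle -1 drug follows odd/even subject number with no visible concealment, so any thalidomide-versus-lenalidomide contrast in the correlative studies is open to selection

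*Combined protocol and SAP*

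**What the plan says.** The Schema and Section 5.1 give the same rule for Cycle -1. Section 5.1 states "Half of the patients (odd numbered subjects) will start with a two week course of single agent thalidomide"; the dosing summary in the Schema states "odd numbered subjects will receive thalidomide and even numbered subjects will receive lenalidomide". Section 5.1 also describes the setting: "This is an open label, phase II, single arm, and single institution study".

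The split serves the correlative work. The Schema says of it: "This will allow the study of correlative samples of monotherapy with either IMiD™ agent". Section 1.2 makes that work a secondary objective: "To perform correlative studies to determine the potential mechanism of action of how thalidomide and lenalidomide are affecting CLL lymphocytes".

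Sampling in the lead-in is repeated within each patient. The RNA arrays in Section 9, for instance, are scheduled as "CLL cells: day 1, 2, and 15 of cycles -1 and 1 prior to administration of study drug", and most of the other lead-in assays are drawn on Days 1 and 15. From Cycle 1 every patient is scheduled to receive both oral drugs plus rituximab.

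No visible passage mentions random assignment, concealment or stratification for the lead-in. Most of Section 4, on central registration, is redacted, so how and when subject numbers are issued cannot be seen. Section 13 gives no analysis for the correlative studies and no comparison of the two lead-in groups.

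**The concern.** A parity rule is deterministic. Where numbers run in order at a single open-label site, the people registering patients can work out the next lead-in drug from the last number used. Section 3 allows screening up to 28 days before therapy, which leaves room to choose the order in which eligible patients are registered.

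The protocol itself supplies reasons why a careful clinician might want to choose:

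- Section 5.5.1 reports tumor lysis in CLL patients given lenalidomide and places the highest risk in the first cycle.
- Section 5.1 ties the lenalidomide starting dose to creatinine clearance.
- Section 2.5 names neuropathy as a limiting toxicity of thalidomide, and Section 3.2 excludes pre-existing neuropathy only from grade 2 upward.

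Cycle -1 is the only scheduled window in which each drug is given alone. If patients were sorted by burden, renal function or neuropathy, a difference between the two groups in a marker or expression profile could reflect who was treated and not which drug they took.

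**Working it through.** **1. The plan's own figure.** Section 13.1 gives a Simon minimax design with p0 = 0.60, p1 = 0.80, 10% significance and 80% power. It stops at 6 or fewer responders among 11 and succeeds at 18 or more among 24. With b(k; 11, p) the binomial probability of k responders in stage 1,

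P(success) = sum over k = 7 to 11 of b(k; 11, p) × P(Bin(13, p) ≥ 18 − k).

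- At p = 0.60 this is 0.0930, and the chance of early stopping is 0.467.
- At p = 0.80 this is 0.8015, and the chance of early stopping is 0.050.
- A search for the smallest N meeting both limits returns 6/11 and 17/24.

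The design reproduces. It pools all patients, so the way the lead-in drug is assigned does not enter it.

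**2. Predictability of the next lead-in drug.** The measure is the expected number of correct guesses in 24, when the guesser always names the drug with more places left. The block sizes are assumptions to show the range.

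| Method | Correct of 24 | Share |
|---|---|---|
| Odd/even, numbers in sequence | 24 | 100% |
| Permuted blocks, known size 4 | 17.0 | 71% |
| Permuted blocks, known size 6 | 16.4 | 68% |
| One random 12:12 list | 14.6 | 61% |
| Simple randomisation | 12 | 50% |

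For a block of 4, the first guess scores 1/2 and the second 2/3. With probability 2/3 one place remains for each drug, and the last two guesses score 1.5. With probability 1/3 both places are for the same drug, and they score 2. The sum is 0.5 + 0.667 + (2/3)(1.5) + (1/3)(2) = 2.833, and six blocks give 17.0. Someone who does not know the sizes cannot do better on average than someone who does, so 71% and 68% are upper bounds for concealed blocks of those sizes.

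**3. What a little sorting would do.** As an assumption, take 12 high-burden patients among 24, otherwise split 6 and 6. Exchanging two with the other group gives 8/12 against 4/12, a gap of 33 points. Exchanging three gives 9/12 against 3/12, a gap of 50 points. For scale, at 50% prevalence and with independent groups, the standard error of the difference from chance alone is √(2 × 0.5 × 0.5 / 12) = 0.204, about 20 points.

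**4. What a between-drug contrast could show.** With 12 per group, a two-sided 5% test has 80% power for (1.960 + 0.842) × √(2/12) = 1.14 SD (normal approximation). Only very large differences would be detectable even with perfect allocation.

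**The case against.** The strongest reply is that the exposed comparison is not in the protocol. The study is single arm, Section 13 states no between-drug hypothesis or test, and lead-in samples are taken before and after treatment in the same patient. This largely stands. Each patient's own baseline removes differences in starting level. It does not remove differences in the size of change that depend on burden or renal function, so the protection is partial.

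A second reply is that the numbering procedure is redacted and a central registration step exists. This also stands. A reader might infer that staff always know the next drug; the documents support that only if numbers are issued in sequence and the last one is known before registration.

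Third, the incentive to steer is modest. All patients are due to receive lenalidomide from Cycle 1, and tumor lysis prophylaxis is required for everyone before Cycle -1. A reader might also point to tumor flare as a reason to steer patients from one drug to the other, but Section 5.2 describes flare with both. Tumor lysis is the better example. Nothing in the documents shows that steering took place.

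Fourth, chance imbalance is already large at 12 per group, and randomisation would not remove it. That is true, but chance imbalance has no preferred direction and is allowed for in the usual standard error; selection is not.

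Finally, a reader might treat the lead-in as the trial's only drug-specific information. Sections 6.1 and 6.2 also attribute toxicity to the individual agent, so that goes too far.

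**Conclusion.** The point holds as a minor design weakness. Lead-in assignment is deterministic and, in the visible text, unconcealed. If numbers run in sequence, predictability is 100%, against 50% for a simple random list and about 68% to 71% for blocks of known size 6 or 4. The documents show an opportunity for selection, not its occurrence, and the two or three exchanged patients in the illustration are assumed.

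Its reach is limited to thalidomide-versus-lenalidomide contrasts in the correlative studies. These would be exploratory in any case, because none is specified and only differences of about 1.14 SD are detectable. A reader might infer that the response rate is compromised. It is not: N = 24, the stopping rule and the pooled primary endpoint do not depend on which drug came first in the lead-in.

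**What to change.** **For patients not yet enrolled:** replace the odd/even rule with a concealed 1:1 random list, either simple or in permuted blocks of undisclosed, varying size. Central registration should hold it and release each assignment only after eligibility is confirmed. Simple randomisation gives the lowest predictability but may leave the groups unequal; blocks keep them close to 12 and 12.

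**For patients already assigned by parity:** a list cannot help them. State how subject numbers were issued. Tabulate by lead-in drug the baseline features already collected: creatinine clearance, FISH, IgVH status, beta-2-microglobulin and disease burden. Label any between-drug contrast non-randomised and exploratory.

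**Cost:** a list of at most 24 lines and a protocol amendment, which under Section 12.1 needs the Principal Investigator's agreement, review by the supporting company and IRB approval. Sample size, visits and the regimens themselves do not change. Appendix H cites a 2016 safety board decision, so accrual may be well advanced or complete; the documents do not say. If it is complete, only the reporting steps apply.

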  - Creatinine clearance of  $\geq 30$  mL/min by Cockcroft-Gault formula (see Appendix E). Patients with a baseline creatinine clearance of  $\geq 30$  and  $\leq 60$  mL/min will have a starting dose of lenalidomide 5 mg PO every other day per the defined schedule. Patients with a baseline creatinine clearance of  $\geq 60$  mL/min will have a starting dose of lenalidomide 5 mg PO daily per the defined schedule (see Section 5 for details).
  - Total bilirubin  $\leq 1.5$  times the ULN, unless abnormality is the result of Gilbert's disease or the result of the CLL

- AST (SGOT) and ALT (SGPT)  $\leq 3 \times$  ULN (or  $\leq 5 \times$  ULN if due to the CLL)
9. Disease free of prior malignancies for  $\geq 2$  years with exception of curatively treated basal cell carcinoma, squamous cell carcinoma of the skin, or carcinoma “in situ” of the cervix or breast.
  10. All study participants must be registered into the mandatory Revlimid REMS® and S.T.E.P.S.® ( P-TAP: Protocol Therapy Assistance Program) program(s), and be willing and able to comply with the requirements of Revlimid REMS® and S.T.E.P.S.®.
  11. Females of childbearing potential (FCBP)† must have a negative serum or urine pregnancy test with a sensitivity of at least 25 mIU/mL within 10 – 14 days prior to and again within 24 hours of starting treatment and again within 24 hours before the first dose of lenalidomide AND thalidomide. FCBP must either commit to continued abstinence from heterosexual intercourse or begin TWO acceptable methods of birth control, one highly effective method and one additional effective method AT THE SAME TIME, at least 28 days before she starts taking lenalidomide and/or thalidomide. Females of reproductive potential must adhere to the scheduled pregnancy testing as required in the Revlimid REMS® program . Men must agree to use a latex condom during sexual contact with a FCBP even if they have had a successful vasectomy. All patients must be counseled at a minimum of every 28 days about pregnancy precautions and risks of fetal exposure. See Appendix A: Risks of Fetal Exposure, Pregnancy Testing Guidelines and Acceptable Birth Control Method..
  12. Able to take aspirin 81 or 325 mg daily as prophylactic anticoagulation, unless already on therapeutic anticoagulation. Patients intolerant to ASA may use coumadin or low molecular weight heparin.

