### 5.4 Drug Administration

#### 5.4.1 Dosing regimen

- Cycle -1: patients will receive thalidomide 50 mg PO daily on days 1-14 or lenalidomide PO on days 1-14, followed by no treatment days 15-28, as described previously in 5.1.
- Cycle 1 and subsequent cycles: Patients will receive thalidomide 50 mg (every **ODD** day on days 1-28 of a 28 day cycle) with lenalidomide (every **EVEN** day on days 1-28 of a 28 day cycle), as described previously. Each cycle will be 28 days in length.
- Cycle 1: Patients will also receive rituximab 375 mg/m^2 IV on Days 1, 8, 15 and 22 and then again on the same weekly x 4 schedule every 6th cycle through Cycle 19 (Cycle 7, 13, and 19), as described previously.

Patients unable to tolerate either thalidomide or lenalidomide will be removed from protocol. Patients unable to tolerate rituximab can continue on with protocol treatment without additional rituximab being administered.

Dosing of thalidomide and lenalidomide should be at bedtime in order to allow for the sedative effects of thalidomide to not cause daytime somnolence and to maintain regular dosing intervals. **Only enough lenalidomide for one cycle of therapy will be supplied to the patient each cycle.** At the start of any non-clinic visit treatment cycles subsequent to Cycle 24, one cycle of study drug will be shipped to the subject.

See Section 5.5 for allopurinol and oral hydration requirements as prophylaxis against tumor lysis syndrome (TLS).

Thalidomide and lenalidomide capsules should be swallowed whole, and should not be broken, chewed or opened.

If a dose of thalidomide or lenalidomide is missed, it should be taken as soon as possible on the same day. If it is missed for the entire day, it should not be made up.

Patients who take more than the prescribed dose of thalidomide or lenalidomide should be instructed to seek emergency medical care if needed and contact study staff immediately.

Subjects experiencing adverse events may need study treatment modifications (See section 5.6).

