## 9. CORRELATIVE/SPECIAL STUDIES

See Section 5.1 for specific dosing instructions

**Cycle -1:** Half of the patients will receive 14 days of thalidomide 50 mg PO daily, followed by 14 days off and the other half of the patients will receive 14 days of lenalidomide 5 mg PO daily, followed by 14 days off

**Cycle 1 and beyond:** Alternating thalidomide and lenalidomide continuously

Samples will be collected for correlative studies to be performed in association with the trial. The following samples will be collected:

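### The Section 5.1 footnote contradicts itself on the Cycle -1 lenalidomide schedule; read as daily, it cancels the renal reduction for creatinine clearance 30 to <60 mL/min

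*Combined protocol and SAP*

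**What the plan says.** In Cycle -1, even-numbered subjects take lenalidomide alone for 14 days and then have 14 days off. The places that bear on the schedule are these.

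- **Section 5.1, Cycle -1 bullet.** Lenalidomide is daily on Days 1–14, and "The lenalidomide dose will be based on baseline calculated creatinine clearance".
- **Section 5.1, starting-dose table.** Clearance ≥60 mL/min: 5 mg on every even day. Clearance ≥30 and <60: 5 mg on every second even day.
- **Section 5.1, double-asterisk footnote.** The Cycle -1 dose is the one in the table, restated as 5 mg on alternate days or on every second "EVEN day depending on baseline calculated creatinine clearance) taken daily on Days 1 – 14 of the 28-day cycle".
- **Section 5.1, Cycle 1 bullet.** "Patients who received lenalidomide during Cycle -1 will receive the same dose of lenalidomide starting with Cycle 1".
- **Section 3.1, item 8.** The lower clearance band "will have a starting dose of lenalidomide 5 mg PO every other day per the defined schedule"; the upper band "will have a starting dose of lenalidomide 5 mg PO daily per the defined schedule". It refers to Section 5 for details.
- **Section 5.4.1.** "patients will receive thalidomide 50 mg PO daily on days 1-14 or lenalidomide PO on days 1-14". The word daily is attached to thalidomide only, and the bullet points back to Section 5.1.
- **Section 9.** "the other half of the patients will receive 14 days of lenalidomide 5 mg PO daily, followed by 14 days off", with no split by renal function, under the line "See Section 5.1 for specific dosing instructions".
- **Schema.** Daily on Days 1–14, with no dose given for lenalidomide.

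**The concern.** The footnote is the only place that says how the clearance-based table applies to Cycle -1, and its two halves cannot both be followed. Sections 3.1, 5.4.1 and 9 refer the reader back to Section 5 or 5.1, so the cross-references lead to the contradiction and do not settle it.

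The conflict matters most for clearance 30 to <60. Both bands start at 5 mg and differ only in frequency. Capsules are 5 mg or 25 mg (Section 8.1.5) and must be swallowed whole (Section 5.4.1), so a smaller daily amount is not available. If frequency is overridden by daily dosing, nothing remains of the renal adjustment.

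This is these patients' first exposure to a drug that is about two-thirds excreted unchanged in urine in healthy volunteers (Section 8.1.3). Section 5.5.1 places the highest tumor lysis risk in the first cycle, and Section 2.5 calls the toxicities of both agents dose related. Cycle -1 also exists to supply monotherapy correlative samples, so an unclear schedule means that Day 15 samples could follow different exposures within one renal band.

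**Working it through.** The plan states no cumulative Cycle -1 dose, so there is no figure to reproduce. The check is a count of dosing days.

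**Inputs.** 5 mg per administration (Section 5.1 table, Section 9); a 14-day window (Section 5.1); frequencies as listed above.

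**Formula.** Cumulative dose = number of dosing days × 5 mg.

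**Clearance 30 to <60, Cycle -1 Days 1–14**

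| Reading | Source | Dosing days | Total |
|---|---|---|---|
| Daily | Footnote ending; Section 5.1 bullet; Section 9; Schema | 14 | 14 × 5 = 70 mg |
| Every other day | Section 3.1, item 8 | 7 | 7 × 5 = 35 mg |
| Every second even day | Footnote parenthesis; Section 5.1 table | 4 (Days 2, 6, 10, 14) or 3 (Days 4, 8, 12) | 20 or 15 mg |

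Ratios: 70/35 = 2.0; 70/20 = 3.5; 70/15 = 4.7.

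**Clearance ≥60, same window.** Even days only: 7 × 5 = 35 mg. Daily: 14 × 5 = 70 mg. The footnote conflicts here too, but Section 3.1, Section 9, the Section 5.1 bullet and the Schema all point to daily.

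**Which reading fits best?** Compare each band's dose count with the Section 5.1 table over a full 28-day cycle.

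- Table: ≥60, 14 even days, 14 × 5 = 70 mg; 30 to <60, every second even day, 7 × 5 = 35 mg.
- Section 3.1 frequencies applied to the 14 dosing days of Cycle -1: ≥60, daily, 14 doses, 70 mg; 30 to <60, every other day, 7 doses, 35 mg.

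The counts agree in both bands, and the 2:1 ratio between bands is kept. This mapping also explains how the footnote may have come about. Cycle -1 has no alternating partner drug, so the even-day slots become consecutive days: every even day turns into daily, and every second even day turns into every other day. The protocol does not say this, so it is the likeliest intent and not a documented one.

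The other two readings fit less well. Daily dosing for both bands leaves Section 5.1's clearance-based dose with no effect. Every second even day, taken literally, contradicts all the daily wording as well as Section 3.1, and it places an even-day calendar on a cycle with nothing to alternate.

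**The case against.** **The readings are not equally supported.** This stands. A reader might infer an open three-way choice with up to a 4.7-fold spread in dose. The documents do not support that. The 3.5- to 4.7-fold contrast uses the least supported reading as its base. The requirement to carry the same dose into Cycle 1 does not rescue that reading, because the phrase can mean 5 mg per administration. If it also fixed frequency, the ≥60 band would be on even days in Cycle -1, against most of the text. The contrast that matters is 70 against 35 mg.

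**Section 3.1 is an eligibility item and does not name Cycle -1.** True. That is why its frequencies need clinical confirmation before they are adopted.

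**Harm is inferred, not shown.** Largely true. No reading gives more than 5 mg at once. The 70 mg total equals a 28-day cycle at Dose Level 1, which is this band's first titration step, and the band may later reach 15 mg on every even day, 14 × 15 = 210 mg per cycle. Against that, titration requires a tolerated prior cycle, and Cycle -1 would put the 70 mg into 14 days. Section 8.1.3 reports no accumulation on multiple dosing at the recommended regimen and a half-life of about 3 hours, the latter alongside healthy-volunteer data. The documents give no data for reduced clearance.

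**Safeguards exist.** Laboratory tumor lysis at entry is excluded until corrected (Section 3.2). Allopurinol and hydration are required (Section 5.5.1). Section 10 schedules chemistries on Days 1, 4, 8, 11, 15 and 22 of Cycle -1, and Grade 2 or higher tumor lysis stops treatment. These limit the consequences, but none tells the prescriber which schedule to use.

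**The text may no longer matter.** Appendix H shows that this version follows one dated September 2013 and cites an August 2016 DSMB meeting. Enrolment status is not stated, so whether anyone will still start Cycle -1 under it is unknown.

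**Conclusion.** The footnote is wrong as written. It is an internal contradiction in a dosing rule, not a design choice, and of moderate severity. For even-numbered subjects with clearance 30 to <60, following it as daily gives 70 mg over Days 1–14, against 35 mg under Section 3.1. That is a two-fold difference, and it removes the renal reduction at first exposure.

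The number affected is bounded by half of 24, so at most 12, and may be zero, because the documents do not give the number in this clearance band.

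Two further inferences should be resisted. The documents do not show that any patient was overdosed or harmed, since the schedule actually given is not reported. Nor does the contradiction reach the primary endpoint, the sample size or the operating characteristics of the Simon design, none of which depends on the Cycle -1 lenalidomide schedule as specified.

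The conclusion rests on 5 mg per administration, as stated throughout for the starting dose. The choice of the Section 3.1 mapping rests on its match with the table's dose counts of 14 and 7, and remains subject to clinical confirmation.

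**What to change.** Replace the double-asterisk footnote in Section 5.1 with:

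*Cycle -1, Days 1–14: clearance ≥60 mL/min, 5 mg daily; clearance ≥30 and <60 mL/min, 5 mg every other day.*

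Have the clinical team confirm that this was the intent before it is adopted. Then make the Schema, the Section 5.1 bullets, Section 5.4.1 and Section 9 match. In Section 5.1, state that the carry-over into Cycle 1 is of the 5 mg dose, with the table's even-day frequency applying from then on.

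If Cycle -1 enrolment is already complete, document the schedule actually given to each even-numbered subject by clearance band, so that safety data and the monotherapy correlative samples can be read against true exposure.

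The cost is one clinical confirmation and amendment wording, plus a review of dosing records if enrolment is complete. Sample size, visits and procedures do not change.
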